# 7.2.7.2 Recording Adverse Events

Adverse events are to be recorded on the AE page of the eCRF. Severity will be graded according to the following definitions:

Protocol No.: TEN-02-401

Edition No.: 1

 Mild: The patient experiences awareness of symptoms but these are easily tolerated or managed without specific treatment

- Moderate: The patient experiences discomfort enough to cause interference with usual activity, and/or the condition requires specific treatment
- Severe: The patient is incapacitated with inability to work or do usual activity, and/or the event requires significant treatment measures.

Action taken will be categorized as dose not changed, dose reduced, drug interrupted, drug withdrawn, required concomitant medication, required concomitant procedure and/or other.

Event outcome at resolution or time of last follow-up will be recorded as not recovered/not resolved, recovered/resolved with sequelae, recovering/resolving, fatal or unknown.

#### 7.2.7.3 Assessment of Adverse Events

The relationship of the event to the study drug should be determined by the Investigator according to the following criteria:

- Not related: The event is most likely produced by other factors such as the patient's
  clinical condition, intercurrent illness, or concomitant drugs, and does not follow a known
  response pattern to the study drug, or the temporal relationship of the event to study drug
  administration makes a causal relationship unlikely
- Possibly related: The event follows a reasonable temporal sequence from the time of drug administration, and is possibly due to drug administration and cannot be reasonably explained by other factors such as the patient's clinical condition, intercurrent illness, or concomitant drugs.
- Related: The event follows a reasonable temporal sequence from the time of drug
  administration, and/or follows a known response pattern to the study drug, and cannot be
  reasonably explained by other factors such as the patient's clinical condition, intercurrent
  illness, or concomitant drugs.

# 7.2.7.4 Following Adverse Events

All (both serious and non-serious) AEs must be followed until they are resolved or stabilized, or until all attempts to determine resolution of the event are exhausted. The Investigator should use his/her discretion in ordering additional tests as necessary to monitor the resolution of such events.

Protocol No.: TEN-02-401

Edition No.: 1

#### 7.2.7.5 Discontinuation due to Adverse Events

Any patient who experiences an AE may be withdrawn at any time from the study at the discretion of the Investigator. Patients withdrawn from the study due to an AE, whether serious or non-serious, must be followed by the Investigator until the clinical outcome of the AE is determined. The AE(s) should be noted on the appropriate CRFs and the patient's progress should be followed until the AE is resolved. A decision to discontinue a patient due to an AE should be discussed with the Medical Monitor. If the AE may relate to overdose of study treatment, the IB should be consulted for details regarding any specific actions to be taken.

#### 7.2.7.6 Pregnancy

Female patients must be instructed to discontinue tenapanor and inform the study Investigator immediately if they become pregnant during the study.

The Investigator must report any pregnancy to within 1 business day of becoming aware of it. The patient must be immediately discontinued from further treatment with tenapanor. An uncomplicated pregnancy will not be considered an AE or SAE, but all pregnancies will be followed through birth.

Pregnancies are captured if they occur in female patients or in the sexual partners of male patients from the time the patient is first exposed to tenapanor until 30 days after last exposure.

Any congenital abnormalities in the offspring of a patient who received study drug will be reported as an SAE. The outcome of any pregnancy and the presence or absence of any congenital abnormality will be recorded in the source documentation and reported to

#### 7.2.7.7 Serious Adverse Events

An SAE is any AE occurring from Enrollment through final study visit (V13), at any dose that results in any of the following outcomes:

- Death
- A life-threatening adverse drug experience
- Inpatient hospitalization or prolongation of existing hospitalization
- A persistent or significant disability/incapacity
- A congenital anomaly/birth defect

Protocol No.: TEN-02-401

Edition No.: 1

Important medical events that may not result in death, be life threatening, or require hospitalization may be considered an SAE when, based upon appropriate medical judgment, they may jeopardize the patient and may require medical or surgical intervention to prevent any of the outcomes listed in this definition. Examples of such medical events include allergic bronchospasm requiring intensive treatment in an emergency room or at home, blood dyscrasias or convulsions that do not result in inpatient hospitalization, or the development of drug dependency or drug abuse.

Note: SAEs require immediate reporting to

Adverse Events" below for details.

# 7.2.7.8 Reporting Serious Adverse Events

In the event of any SAE reported or observed during the study, whether or not attributable to the study drug, site personnel will report it to within 24 hours of the knowledge of the occurrence.

To report the SAE, complete the SAE form electronically in the electronic data capture (EDC) system for the study. When the form is completed, will be notified electronically and will retrieve the form. If the event meets serious criteria and it is not possible to access the internet, send an email to at or call the possible to access the internet, send an email to at or call the possible to access the internet, send an email to at at or call the possible to access the internet, send an email to at at at a possible to access the internet, send an email to at at at a possible to access the internet, send an email to at at at a possible to access the internet, send an email to at a possible to access the internet, send an email to at a possible to access the internet, send an email to at a possible to access the internet, send an email to at a possible to access the internet, send an email to at a possible to access the internet, send an email to at a possible to access the internet, send an email to at a possible to access the internet, send an email to a possible to access the internet, send an email to a possible to access the internet, send an email to a possible to access the internet, send an email to a possible to access the internet, send an email to a possible to access the internet, send an email to a possible to access the internet, send an email to a possible to access the internet, send an email to a possible to access the internet, send an email to a possible to access the internet, send an email to a possible to access the internet, send an email to a possible to access the internet, send an email to a possible to access the internet, send an email to a possible to access the internet, send an email to a possible to access the internet, send an email to a possible to access the internet, send an email to a possible to access the internet, send an email to a possible to access the internet, send an email to a possible to access the internet, send an email to a possible to access the internet, send a

Safety Contact Information:

The Investigator is required to submit SAE reports to the Institutional Review Board (IRB)/Independent Ethics Committee (IEC) in accordance with local requirements. All investigators involved in trials using the same investigational product will receive any safety

Protocol No.: TEN-02-401

Edition No.: 1

alert notifications for onward submission to their local IRB/IEC as required. All reports sent to investigators will be blinded.

## Follow-Up Reports

The Investigator must continue to follow the patient until the SAE has resolved or until the condition becomes chronic in nature, stabilizes (in the case of persistent impairment) or the patient dies.

Within 24 hours of receipt of follow-up information, the Investigator must update the SAE form electronically in the EDC system for the study and submit any supporting documentation (e.g., patient discharge summary or autopsy reports) to via fax or e-mail. If it is not possible to access the EDC system, refer to the procedures outlined above for initial reporting of SAEs.

## 7.3 Efficacy Variables

The following are the efficacy variables for this study:

- Patients reaching serum phosphorus goal levels defined as sP>2.5 and ≤4.5 mg/dL
- Patients reaching serum phosphorus goal levels defined as  $sP \le 4.5 \text{ mg/dL}$
- Percent change from baseline in sevelamer dose
- Change from baseline in iFGF23 (intact)
- Change from baseline in Kidney Disease and Quality of Life survey (KDQoL) composite score and subscales
  - Kidney Disease and Quality of Life™ (KDQOL™-36) (Copyright© 2000 by RAND and the University of Arizona)
- Change from baseline in Dialysis Symptom Index survey (DSI) overall symptom burden score and overall symptom severity score
  - The University of Pittsburgh Medical Center, VA Pittsburgh Healthcare System (Weisbord et al. J Pain Symptom Manage, 2004:27, 226-40.)

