#### **Tenapanor Arm**

The dosing regimens described below for sevelamer are for guidance to the Investigators. Investigators have flexibility to dose sevelamer, TID, BID or QD based on their experience with each patient or as per package insert. Dosing regimens can be adjusted based on the most recent sP laboratory data (central laboratory data or standard of care local laboratory data).

If patients are in the tenapanor arm (from the TEN-02-301 study), sevelamer will be added as described below:

- $sP \ge 2.5$  and  $\le 4.5$  mg/dL: no addition of sevelamer.
- sP >4.5 and  $\leq$ 5.0 mg/dL: add one 800 mg tablet QD.
- sP > 5.0 and  $\leq 5.5$  mg/dL: add one 800 mg tablet BID.
- sP >5.5 mg/dL: add one 800 mg tablet TID.

Protocol No.: TEN-02-401

Edition No.: 1

If sP is still greater than or becomes >4.5 mg/dL at a subsequent visit, sevelamer dose can be increased in a stepwise manner as described below:

- sP >4.5 and ≤5.0 mg/dL: add one 800 mg tablet to the existing regimen.
- sP >5.0 and ≤5.5 mg/dL: add two 800 mg tablets to the existing regimen.
- sP >5.5 mg/dL: add three 800 mg tablets each day (800 mg TID) to the existing regimen.

The maximum dose of sevelamer should be based on standard of care, the sevelamer package insert, and the Investigator's experience with each patient.

If sP <2.5 mg/dL at any visit

- Sevelamer dose can be lowered by one 800 mg tablet TID, or as appropriate, based on current regimen; Investigators have flexibility to dose sevelamer BID or QD based on their experience with each patient or as per package insert.
- If patient is not taking sevelamer then tenapanor dose can be lowered by one 10 mg tablet BID, unless already at tenapanor 10 mg BID, then can dose tenapanor 10 mg QD

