#### 3 STUDY OBJECTIVES

# 3.1 Primary Objectives

The primary objective of this study is:

 To evaluate the ability of tenapanor alone or in combination with sevelamer to achieve serum phosphorus concentration (sP) within the population reference range (sP ≥2.5 and ≤4.5 mg/dL) in patients with end-stage renal disease on dialysis with hyperphosphatemia (>4.5 mg/dL).

Protocol No.: TEN-02-401

Edition No.: 1

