#### **Tenapanor Arm**

The dosing regimens described below for sevelamer are for guidance to the Investigators. Investigators have flexibility to dose sevelamer, TID, BID or QD based on their experience with each patient or as per package insert. Dosing regimens can be adjusted based on the most recent sP laboratory data (central laboratory data or standard of care local laboratory data).

If patients are in the tenapanor arm (from the TEN-02-301 study), sevelamer will be added as described below:

- $sP \ge 2.5$  and  $\le 4.5$  mg/dL: no addition of sevelamer.
- sP > 4.5 and  $\leq 5.0$  mg/dL: add one 800 mg tablet QD.
- sP > 5.0 and  $\leq 5.5$  mg/dL: add one 800 mg tablet BID.
- sP > 5.5 mg/dL: add one 800 mg tablet TID.

If sP is still greater than or becomes >4.5 mg/dL at a subsequent visit, sevelamer dose can be increased in a stepwise manner as described below:

- sP >4.5 and  $\le$ 5.0 mg/dL: add one 800 mg tablet to the existing regimen.
- sP > 5.0 and  $\leq 5.5$  mg/dL: add two 800 mg tablets to the existing regimen.
- sP > 5.5 mg/dL: add three 800 mg tablets each day (800 mg TID) to the existing regimen.

The maximum dose of sevelamer should be based on standard of care, the sevelamer package insert, and the Investigator's experience with each patient.

If sP < 2.5 mg/dL at any visit

- Sevelamer dose can be lowered by one 800 mg tablet TID, or as appropriate, based on current regimen; Investigators have flexibility to dose sevelamer BID or QD based on their experience with each patient or as per package insert.
- If patient is not taking sevelamer then tenapanor dose can be lowered by one 10 mg tablet BID, unless already at tenapanor 10 mg BID, then can dose tenapanor 10 mg QD

Protocol No.: TEN-02-401

Edition No.: 1

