#### **Tenapanor Arm**

The dosing regimens described below for sevelamer are for guidance to the Investigators. Investigators have flexibility to dose sevelamer, TID, BID or QD based on their experience with each patient or as per package insert. Dosing regimens can be adjusted based on the most recent sP laboratory data (central laboratory data or standard of care local laboratory data).

If patients are in the tenapanor arm (from the TEN-02-301 study), sevelamer will be added as described below:

- sP ≥2.5 and ≤4.5 mg/dL: no addition of sevelamer.
- sP >4.5 and ≤5.0 mg/dL: add one 800 mg tablet QD.
- sP >5.0 and ≤5.5 mg/dL: add one 800 mg tablet BID.
- sP >5.5 mg/dL: add one 800 mg tablet TID.

If sP is still greater than or becomes >4.5 mg/dL at a subsequent visit, sevelamer dose can be increased in a stepwise manner as described below:

Protocol No.: TEN-02-401

Edition No.: 1

- sP >4.5 and  $\leq$ 5.0 mg/dL: add one 800 mg tablet to the existing regimen.
- sP > 5.0 and  $\le 5.5$  mg/dL: add two 800 mg tablets to the existing regimen.
- sP >5.5 mg/dL: add three 800 mg tablets each day (800 mg TID) to the existing regimen.

The maximum dose of sevelamer should be based on standard of care, the sevelamer package insert, and the Investigator's experience with each patient.

If sP < 2.5 mg/dL at any visit

- Sevelamer dose can be lowered by one 800 mg tablet TID, or as appropriate, based on current regimen; Investigators have flexibility to dose sevelamer BID or QD based on their experience with each patient or as per package insert.
- If patient is not taking sevelamer then tenapanor dose can be lowered by one 10 mg tablet BID, unless already at tenapanor 10 mg BID, then can dose tenapanor 10 mg QD

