#### **Sevelamer Arm**

If patients are from the TEN-02-301 sevelamer arm, tenapanor dose will be added based on their baseline sP as described below. Investigators may decrease or increase the tenapanor dose based on sP levels and/or GI tolerability in 10 mg increments to a minimum of 10 mg QD or a maximum of 30 mg BID, not more than once daily. Dosing regimens can be adjusted based on the most recent sP laboratory data (central laboratory data or standard of care local laboratory data).

- sP >2.5 and ≤3.5 mg/dL: add three 10 mg tablets of tenapanor QD and Sevelamer dose can be lowered by one 800 mg tablet TID.
- sP > 3.5 and  $\leq 4.5$  mg/dL: add three 10 mg tablets of tenapanor QD
- sP >4.5: add three 10 mg tablets of tenapanor BID

If sP >4.5 mg/dL at next visit

 add three 10 mg tenapanor tablets, if on QD regimen to a maximum of 30 mg tenapanor BID. If on 30 mg tenapanor BID follow sevelamer dose regimen changes described below

Sevelamer dose can be increased by at least one 800 mg tablet at the largest meal and up to one 800 mg tablet TID; Investigators have flexibility to dose sevelamer BID or QD based on their experience with each patient or as per package insert. If sP < 2.5 mg/dL at any visit:

Protocol No.: TEN-02-401

Edition No.: 1

Sevelamer dose can be lowered by one 800 mg tablet TID; Investigators have flexibility
to dose sevelamer BID or QD based on their experience with each patient or as per
package insert.

• If patient is not taking sevelamer then tenapanor dose can be lowered by one 10 mg tablet BID, unless already at tenapanor 10 mg BID, then can dose tenapanor 10 mg QD.

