# 9.2 Determination of Sample Size

Approximately 150-200 patients with ESRD on hemodialysis (HD) or peritoneal dialysis (PD) will be enrolled in this study. The sample size of this study is not planned based on statistical considerations.

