#### 9.4.3 Efficacy Analysis

All efficacy variables will be descriptively summarized at each visit for the FAS and each TEN-02-301 treatment arm (tenapanor or sevelamer). Descriptive summaries of sP variables will also be repeated for FAS subjects with a baseline sP >4.5 mg/dL.

For response endpoints, the response rate at each post-baseline visit will be estimated with asymptotic 95% confidence interval (CI) for each TEN-02-301 treatment arm. Inferential analyses of sP endpoints will be performed for comparisons of phosphorus-lowering effect between monotherapy (tenapanor and sevelamer alone) and combination therapy (tenapanor combined with sevelamer) unless the sample size in each monotherapy treatment group is less than 15. Detailed model specifications will be provided in the statistical analysis plan (SAP). Inferential analyses of other endpoints may be performed as suggested by the data.

Analyses will be detailed in the statistical analysis plan (SAP).

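### Section 7.3 sets the lower bound of the serum phosphorus goal at >2.5 mg/dL, while the primary objective it implements uses ≥2.5; align the two before analysis.

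*Combined protocol and SAP*

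**What the plan says.** Sections 1.2 and 3.1 state the primary objective in the same terms: sP is to be brought "within the population reference range (sP ≥2.5 and ≤4.5 mg/dL"). Both bounds are included.

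Section 7.3 lists six efficacy variables and labels none as primary. The first is "Patients reaching serum phosphorus goal levels defined as sP>2.5 and ≤4.5 mg/dL". It is the only one with both a lower and an upper bound, so it is the only one that can implement the primary objective. The second, sP ≤4.5 mg/dL, has no lower bound and corresponds to a secondary objective.

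The analysis is descriptive. Under Section 9.4.3, "the response rate at each post-baseline visit will be estimated with asymptotic 95% confidence interval (CI) for each TEN-02-301 treatment arm". Section 9.2 gives the size: "Approximately 150-200 patients with ESRD on hemodialysis (HD) or peritoneal dialysis (PD) will be enrolled in this study". It adds that this number has no statistical basis.

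The value 2.5 also appears in the dose guidance. The tenapanor-arm band includes it ("sP ≥2.5 and ≤4.5 mg/dL: no addition of sevelamer"), and the low-sP rule starts strictly below it ("If sP < 2.5 mg/dL at any visit"). The lowest sevelamer-arm starting band is written with the strict sign ("sP >2.5 and ≤3.5 mg/dL: add three 10 mg tablets of tenapanor QD").

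**The concern.** A response variable should classify every possible value as its objective does. Here one reportable value is classified in opposite ways. Two analysts, one working from 3.1 and one from 7.3, could both follow the protocol and report different counts at any visit where a patient has sP of 2.5.

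The discrepancy has a direction. The set defined by >2.5 lies inside the set defined by ≥2.5, so 7.3 can never give the higher rate. The gap also tends to widen as control improves, because more values then fall near the lower bound. The study is open label (6.3.2), which is a further reason to fix the definition before any rates are tabulated.

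**Working it through.** **Comparison of the definitions**

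| Place | Lower bound | Is sP = 2.5 inside? |
|---|---|---|
| Primary objective, 1.2 and 3.1 | ≥2.5 | Yes |
| Efficacy variable, 7.3 | >2.5 | No |
| Tenapanor-arm band, no sevelamer added (1.2, 4.1.1, 6.1.3) | ≥2.5 | Yes |
| Low-sP rule, both arms (1.2, 4.1.1, 6.1.3) | applies at <2.5 | Rule not triggered |
| Lowest sevelamer-arm starting band (1.2, 4.1.1, 6.1.3) | >2.5 | No |

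The upper bound of 4.5 is included in both the objective and the variable, so the two definitions disagree only at 2.5.

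**Size of the effect**

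The plan has no figure to reproduce: it gives no sP mean or SD, expected response rate or power calculation. The following are assumptions:
- sP is reported to 0.1 mg/dL.
- sP is roughly normal, with on-treatment mean 4.0, 4.5 or 5.0 and SD 1.0, 1.3 or 1.6 mg/dL.

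A reported 2.5 then stands for a true value between 2.45 and 2.55, and the difference between the two response rates is

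P(sP = 2.5) = Φ((2.55 − mean)/SD) − Φ((2.45 − mean)/SD).

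- Smallest case, mean 5.0 and SD 1.0: Φ(−2.45) − Φ(−2.55) = 0.0071 − 0.0054, which is 0.18% before rounding.
- Largest case, mean 4.0 and SD 1.6: Φ(−0.906) − Φ(−0.969) = 0.1824 − 0.1663 = 1.61%.

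| Mean | SD 1.0 | SD 1.3 | SD 1.6 |
|---|---|---|---|
| 4.0 | 1.30% | 1.58% | 1.61% |
| 4.5 | 0.54% | 0.94% | 1.14% |
| 5.0 | 0.18% | 0.48% | 0.74% |

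With both arms together at N = 150 to 200, this is 150 × 0.00176 = 0.26 to 200 × 0.01607 = 3.2 patients per visit. The planned rates are by arm. The documents give no arm sizes; with an assumed 75 to 100 per arm, the range is 75 × 0.00176 = 0.13 to 100 × 0.01607 = 1.6 patients per estimate.

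A wider grid (mean 3.5 to 5.5, SD 1.0 to 1.75) gives 0.04 to 2.4 percentage points. The upper end needs a mean of 3.5.

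**Comparison with sampling error**

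The half-width of the asymptotic 95% interval is 1.96 × √(p(1 − p)/n). For response rates p of 20% to 50%:
- n = 200, p = 0.20: 1.96 × √(0.16/200) = 5.5 points.
- n = 150, p = 0.50: 1.96 × √(0.25/150) = 8.0 points.
- n = 100, p = 0.20: 1.96 × √(0.16/100) = 7.8 points.
- n = 75, p = 0.50: 1.96 × √(0.25/75) = 11.3 points.

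The half-width is thus 5.5 to 8.0 points overall and 7.8 to 11.3 points per assumed arm. Even the 2.4-point shift from the wider grid is smaller than any of these.

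**The case against.** **The SAP may already settle the point.** Section 9.1 gives the SAP precedence where it differs from the protocol, and 9.4.3 sends the analysis detail there. The SAP text is not in the material available, so it may already fix the boundary. This stands as a limit on the consequence. It does not remove the disagreement between 3.1 and 7.3.

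**The sign may be a conversion loss.** The available text was converted from PDF, and an underlined > can lose its line. The last sevelamer-arm starting band reads ≥4.5 in 1.2 and 4.1.1 but >4.5 in 6.1.3. That may be a true inconsistency or a lost mark; the text cannot show which. The same doubt applies to 7.3, so the original must be checked first.

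**The dose guidance is not unanimous.** The tenapanor-arm band and the low-sP rule fit the objective, but the sevelamer-arm starting band uses >2.5. This stands, and the guidance should not be cited as if it uniformly included 2.5. That band guides a starting regimen, however, and does not define response.

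**A stronger reading is tempting.** A reader might infer that the trial's headline response rate fails to measure the primary objective, or that the rates would differ at every visit. The documents support neither. Section 7.3 names no headline variable, and the definitions agree everywhere except at 2.5. In the smallest case above, the expected count is 0.26 patients per visit across both arms, so many visits would show no difference. A patient at 2.5 is also still a responder on the second variable in 7.3. Summing the discrepancy over visits and arms would overstate it, because the rates are planned by visit and by arm.

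**Conclusion.** The inconsistency holds on the available text, subject to the check of the sign. It is a wording error in a response threshold and worth correcting, because the corresponding rate is to be estimated at each post-baseline visit and the strict sign can only lower it.

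The effect is small: about 0.2 to 1.6 percentage points per visit under the stated assumptions on reporting precision, shape, mean and SD, none of which comes from the documents. This is below the confidence-interval half-width in every case considered. No success criterion or sample-size calculation rests on the boundary, so the mismatch does not put the study's conclusions at risk.

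**What to change.** 1. Check the sign in Section 7.3 against the original PDF.
2. If it is a strict inequality, change the first variable in 7.3 to sP ≥2.5 and ≤4.5 mg/dL, to match 1.2 and 3.1.
3. Use the same definition in the SAP before analysis.
4. Separately, reconcile the dose-guidance bands that treat 2.5 differently: ≥2.5 in the tenapanor arm and >2.5 in the sevelamer-arm starting band. This is for those responsible for the dosing sections; no view is offered here on which is right.

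The change to 7.3 is one sign and alters no visit, sample or dose. The cost is administrative. Under 11.5.2, a protocol amendment needs ethics approval unless it is a sponsor-approved logistical or administrative change. If that delays matters, the SAP's precedence under 9.1 means that stating the boundary there settles the analysis, and 7.3 can be corrected at the next amendment.
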